### 6.5.2 Qualitative analysis

After the completion of exit interviews, recordings will be transcribed. Transcripts will be analyzed in NVivo software, using directed content analysis techniques(Merriam and Tisdell 2016) to identify and organize relevant themes. Codes and coding rules for a codebook will be established by the PI and study staff based on the interview guide and transcripts. When the codebook is established, at least two study staff will independently code transcripts to identify themes and sub-themes, resolving disagreements in coding through discussion. Themes will be summarized and compared across demographic groups (e.g. sex, age, race/ethnicity), component-level (e.g., loss- versus gain-framed financial incentives), and diagnosis of prediabetes versus T2D, as well as by intervention effect on MVPA (e.g., more-successful versus less-successful goal achievement by study completion).

### 6.5.3 Exploratory analyses

Demographic characteristics of participants who were excluded after the run-in period (due to MVPA>30 minutes/day or Fitbit wear < 4 days in week 2) will be compared (mean/t-test or median/ranksum for continuous variables, or Fisher's exact test for categorical variables) to participants who were randomized and began the intervention. Adherence to Fitbit wear and syncing will be assessed as number of days with Fitbit data available during the intervention; adherence will be compared across baseline participant characteristics, including demographics, body size measurements, disease (prediabetes or T2D), relative autonomy index, and delay discounting measure.

**Table 1. Analysis plan**

Outcome	Analysis/statistical test
MVPA min/day: baseline vs 6 and 12 weeks ( primary outcome )	Mean/SD or median/IQR, ANOVA/ANCOVA
MVPA min/day: baseline vs 6 and 12 weeks	% of days with $\geq 60$ min/day, Fisher's exact test
MVPA min/day: average per week of intervention	% of days with $\geq 60$ min/day, Fisher's exact test
Steps/day: baseline (2 nd -week of run-in) versus 6 weeks and 12 weeks	Mean/SD or median/IQR, ANOVA/ANCOVA
Steps/day: baseline (2 nd -week of run-in) versus 6 weeks and 12 weeks	% of days with $\geq 10,000$ steps/day, Fisher's exact test
Steps/day: average per week of intervention	% of days with $\geq 10,000$ steps/day, Fisher's exact test
Body mass index Z-score	Mean/SD or median/IQR, ANOVA/ANCOVA
Hemoglobin A1c, insulin, glucose, triglycerides, LDL, HDL, AST, ALT	Mean/SD or median/IQR, ANOVA/ANCOVA
Hemoglobin A1c	% $<5.7\%$ , $5.7\text{-}6.4\%$ , $\geq 6.5\%$ , Fisher's exact test
Healthy Eating Index	Mean/SD or median/IQR, ANCOVA covariate, Pearson/Spearman correlation with demographic variables
Measure of delay discounting, k , derived from MCQ	Mean/SD or median/IQR, ANCOVA covariate (visit 1 measure), Pearson/Spearman correlation with demographic variables, paired t-test or Wilcoxon signed rank test to assess whether baseline and follow-up measures differ
Relative Autonomy Index (RAI) from BREQ-3	Mean/SD or median/IQR, ANCOVA covariate (visit 1 measure), Pearson/Spearman correlation with demographic variables, ANOVA/ANCOVA to assess change from visit 1 to 5 by experimental factor
PACE+: number of days with at least 60 minutes of activity per day in (a) past 7 days and (b) typical week	Mean/SD or median/IQR, Pearson/Spearman correlation with demographic variables and with number of days with MVPA $\geq 60$ minutes at baseline and week 12
Steps/week on smartphone activity tracker	Pearson/Spearman correlation with Fitbit-measured steps/week

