In addition to ANOVA to evaluate effects of the intervention on MVPA at fixed time points (0 versus 12 weeks, 0 versus 6 weeks, Visit 1 versus Visit 5), mixed effects linear regression models will be created, including interactions found to be significant in ANOVA. These models are implemented via maximum likelihood and account for within- and between-subject variability.(Hedeker and Gibbons 2006) Random intercepts will be used to allow for variation between subjects. Sensitivity of the primary analysis to choice of variance model will be examined.

**Table 1** summarizes the analyses planned by outcome measure.

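### Four supporting rows of Table 1 (Analysis plan) apply Fisher's exact test to percentages of days without naming a participant-level unit or a contrast

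*Combined protocol and SAP*

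**What the plan says.** Table 1 (Analysis plan) in Section 6.5.3 has four rows of this kind. Two concern MVPA and give the percentage "of days with $\geq 60$ min/day, Fisher's exact test". Two concern steps and give the percentage "of days with $\geq 10,000$ steps/day, Fisher's exact test". In each pair, one row is labelled baseline versus 6 and 12 weeks. The other is labelled by week, for example "MVPA min/day: average per week of intervention", and names no comparison.

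Other parts of the plan use the participant as the unit:
- The PACE+ row correlates the questionnaire with the "number of days with MVPA $\geq 60$ minutes at baseline and week 12", which is a count per participant.
- The delay-discounting row names a "paired t-test or Wilcoxon signed rank test to assess whether baseline and follow-up measures differ".
- The hemoglobin A1c row also uses Fisher's test, but on one laboratory value per participant with written cut-offs.
- Section 6.5.1 treats the number of subjects per factor level as the sample size that matters.

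The only stated handling of repeated measurements is in the mixed linear models of Section 6.5.1: "Random intercepts will be used to allow for variation between subjects". Those models are not tied to the four rows.

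**The concern.** Fisher's exact test needs a table of independent counts. A participant contributes up to 7 days per week, and an active person tends to be active on several of them. If the table cells hold days, the test overstates the information in the data. If the cells are meant to hold participants, a cut-off on each person's percentage of days is needed, and none is written. For baseline versus week 6 or 12, an unpaired test also ignores that the same people appear on both sides. As written, an analyst must choose both the unit and the contrast, and a p-value below 0.05 in these rows has no known error rate.

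**Working it through.** **Inputs from the documents.** 64 evaluable participants in a balanced 2^4 design (Section 6.6), so 64/2 = 32 per factor level; 7 days in a week, with baseline taken from days 8–14 of the run-in (Section 4.3.1); two-sided alpha 0.05 (Section 6.5.1).

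**Assumed, because the documents do not give them.** ICC of days within a participant, 0.02 to 0.4; share of days over threshold, 1% to 20%.

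**1. The plan's own figure.** The four rows carry none. The stated power reproduces: noncentrality = 15 / (20 × √(1/32 + 1/32)) = 15 / (20 × 0.25) = 3.0. The noncentral t then gives 0.840 (62 df) or 0.836 (48 df), against 0.84 in Table 2. This uses mean MVPA with the participant as unit and does not depend on the four rows.

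**2. Information lost to clustering.** One week gives 64 × 7 = 448 days. Design effect = 1 + (7 − 1) × ICC.

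| ICC | Design effect | Equivalent independent days |
|---|---|---|
| 0.02 | 1.12 | 448/1.12 = 400 |
| 0.1 | 1.6 | 448/1.6 = 280 |
| 0.2 | 2.2 | 448/2.2 = 204 |
| 0.4 | 3.4 | 448/3.4 = 132 |

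**3. Type I error of Fisher's test on days, between factor levels.** Simulation with no true effect, beta-binomial days, 32 v 32 participants, 7 days each:

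| Share of days over threshold | ICC 0.02 | ICC 0.1 | ICC 0.2 | ICC 0.4 |
|---|---|---|---|---|
| 10–20% | 4–5% | 9–12% | 15–17% | 25–27% |
| 3% | 3.2% | 8.0% | 12.6% | 21.2% |
| 1% | 0.7% | 2.9% | 6.6% | 12–13% |

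Fisher's test is conservative with independent days (3.2% in simulation at ICC 0, shares 10% and 30%), so a very small ICC only brings it up to nominal. Simulation error is a few tenths of a point near 5% and about 0.8 points near 25%.

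**4. Fisher's test before versus after in the same 64 participants** (448 v 448 days, shares 10–20%, ICC 0.1–0.4). The result depends on how far a person's propensity carries over between the two weeks: 7–22% at correlation 0.3, 6–14% at 0.6, 3.4–4.4% at 0.9 and 0.6–3.9% at 1.0. The error can go either way.

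**5. Participant-level replacements, shares 10–20%.** ANOVA on change in proportion 3.9–5.4%; ANCOVA adjusted for baseline 4.0–5.8%; paired t-test on change 4.2–5.6%. With only 4–7 valid days per week (shares 3–20%), ANOVA on change gave 3.8–5.4% and the paired t-test 3.8–5.7%. At a 1% share the three methods are conservative (0.4–3.9%). None of these checks imputed days.

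**6. Weekly rows.** Suppose a person's propensity drifts between weeks (assumed week-to-week correlation 0.7–0.9). A random-intercept model then holds for the factor main effect (4–6%) but gives 14–33% for week and factor-by-week tests. One slope per participant holds at 4–5%.

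**The case against.** Pooling of days is the literal reading, but the plan never states it. The PACE+ row and the emphasis on subjects per level in Section 6.5.1 suggest that the team thinks in participants, and a yes/no per participant may have been meant. This stands as a limit on the claim: what is certain is that unit, rule and contrast are missing.

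The 10–20% shares may also be too high for the MVPA rows. Section 4.3.1 excludes a run-in mean above 30 min/day, and Section 1.3 cites 8 to 35 min/day in youth with type 2 diabetes, so days of 60 minutes may be rare, at least at baseline. This stands in part. The exclusion alone does not make them rare: 7 × 30 = 210 minutes leaves room for three such days in a week (3 × 60 = 180). It also sets no direct limit on steps or on later weeks.

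A reader might infer that all 84 intervention days (12 × 7) would be pooled, which would give far larger errors. No row describes that; the weekly rows speak of a weekly average. A reader might also infer that the main result is at risk. It is not: the primary MVPA row and the mean-steps row use ANOVA/ANCOVA on means, and the threshold outcomes are not among the endpoints in Sections 6.1 and 6.2.

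**Conclusion.** The point holds as a specification fault of low severity in four supporting rows. If days are counted as written, a one-week comparison of factor levels has a true error rate near nominal at ICC 0.02, roughly double at 0.1, and about five times nominal at 0.4, for shares of 10–20%. With very rare days and ICC up to 0.1 there is no inflation. A before-after comparison can be inflated or conservative. The sizes rest on assumed ICCs and shares; the missing unit, rule and contrast do not. The documents do not support saying that the team will certainly pool days.

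**What to change.** In the four rows, replace Fisher's test with one value per participant, the proportion of valid days over threshold, and name the contrast.

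- **Baseline rows, by factor level:** analyse the change in proportion, or the week-6 or week-12 proportion adjusted for baseline, with the planned effect-coded ANOVA/ANCOVA.
- **Baseline rows, over time:** use a paired t-test on each participant's change.
- **Weekly rows, factor main effect:** analyse each participant's mean weekly proportion by ANOVA. The random-intercept model is acceptable for this effect only. Section 6.5.1 says "These models are implemented via maximum likelihood"; with 64 participants and a normal reference, that gave 6–7% error with main effects only and 9–10% with all 15 terms, so ANOVA is simpler and safer.
- **Weekly rows, time trend or factor-by-week:** use one slope per participant, or a model with random slopes or serial correlation.
- **Baseline data:** state that baseline proportions use the observed valid run-in days. The imputation predictors in Section 6.5.4 include experimental condition and weeks 1–12, which do not describe the run-in.
- **If a yes/no per participant was meant:** write the cut-off. Fisher's test may then stay, between factor levels only.

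The cost is SAP wording, with the same data and software. Intervals will be wider, and the tests will be conservative if days over threshold are very rare (about 1%); in that case report these outcomes descriptively.

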## ABSTRACT

**Context:** There is an urgent need to engineer targeted physical activity interventions that are effective and scalable for obese adolescents and young adults (AYA) with type 2 diabetes (T2D), who often have very low levels of physical activity. The BEAM Trial is a proposed mobile health (mHealth) intervention that uses behavioral economic-informed financial incentives and text messaging to promote physical activity in AYA with T2D and prediabetes.

**Objectives:** The primary objective is to determine the main and interactive effects of four intervention components (“factors”) on time spent in moderate to vigorous physical activity (MVPA). Secondary objectives include to determine the main and interactive effects of the four intervention components on steps per day, body mass index Z-score; hemoglobin A1c; fasting insulin, glucose, triglycerides, LDL, and HDL; and liver enzymes (AST, ALT).

**Study Design:** 2 full factorial trial; participants randomized to one of 16 experimental conditions (combination of 4 factors with 2 levels each: 1) text messages sent (a) once daily, or (b) twice daily; 2) financial incentives that are (a) loss- or (b) gain-framed; 3) step count goals set as (a) weekly or (b) daily; and 4) step count goal set as (a) ramped or (b) fixed)

**Setting/Participants:** 13-22 year-old AYA who are overweight or obese (BMI $\geq$ 85th percentile for age/sex, or  $\geq$ 25 kg/m^2 if  $\geq$ 18 years old), have prediabetes or type 2 diabetes, and attend the Endocrinology or Adolescent Medicine outpatient clinic at the Children’s Hospital of Pittsburgh; 75 participants will be recruited.

**Study Interventions and Measures:** Vitals, body size measurement, pubertal status, medical history, nutrition, physical activity questionnaires, behavioral questionnaires, and laboratory assessments will be assessed at two in-person study visits; labs (insulin, glucose, hemoglobin A1c, lipids, liver enzymes) will be collected after overnight fast. The primary outcome of MVPA and secondary outcome of step count will be measured using Fitbit physical activity trackers worn daily during a 12-week intervention, which will take place after a 2-week run-in.

---

---

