### **2.2 Secondary Objectives**

The secondary objectives are to:

- Determine the main and interactive effects of the four intervention components on:
  - Daily step count
  - body mass index Z-score
  - hemoglobin A1c
  - fasting insulin
  - fasting plasma glucose
  - fasting triglycerides, LDL, and HDL
  - AST, ALT
- Explore participant-reported intervention acceptability, including constructs of burden, perceived effectiveness, and impact on self-efficacy
- Assess baseline and intervention-related changes in intrinsic versus extrinsic motivation to pursue physical activity
- Assess the association between baseline delay discounting tendency and baseline and change in MVPA and step count
- Assess the correlation between Fitbit-measured physical activity and smartphone-measured physical activity

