### **3.5.1 Inclusion Criteria**

- 1) Males or females age 13 to 22 years.
- 2) Overweight or obese (BMI  $\geq 85^{\text{th}}$  percentile for age/sex, or  $\geq 25 \text{ kg/m}^2$  for participants  $\geq 18$  years)
- 3) Diagnosis with a condition associated with insulin resistance, including prediabetes or type 2 diabetes.
- 4) Consent (subjects 18 and older), Parental/guardian permission (subjects 13-17), assent (subjects 13-17)
- 5) Willingness to wear Fitbit during waking hours daily for duration of run-in and intervention.
- 6) Possession of a smartphone with data plan.

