### 6.2 Secondary Endpoints

Secondary endpoints include main and interactive effects of intervention components on mean steps per day during week 12 of the intervention, and change from visit 1 to visit 5 in:

- body mass index Z-score,
- hemoglobin A1c,
- fasting insulin,
- fasting glucose,
- fasting triglycerides, LDL, HDL, and
- liver enzymes (AST, ALT)

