## 6.5 Statistical Methods

### 6.5.1 Analysis of Primary and Secondary Outcomes of Interest

Descriptive and visual statistics: Demographic and clinical characteristics of subjects will be described using summary statistics, including means, standard deviations, medians, and ranges for continuous variables, and frequencies and percentages of participants for categorical variables. Data will be assessed for outliers. Scatter plots and box plots will be used to examine the relationship between independent (e.g. individual characteristics such as age, prediabetes versus T2D, race/ethnicity; as well as component level, such as gain versus loss-framed incentives) and dependent variables. Line plots will be generated for the primary outcome of daily MVPA, with one line per subject and an overall trend line. Longitudinal data will be summarized by factor level (e.g. loss-framed versus gain-framed incentives). Statistical analyses will be conducted using Stata 17 (StataCorp, College Station, TX) or R: A language and environment for statistical computing (R Corp Team, Vienna, Austria). The significance level for two-sided hypothesis testing will be set at 0.05.

Main Effects and Interactions: The trial is a  $2^4$  full factorial design (4 factors with 2 levels each), resulting in 16 experimental conditions. **Importantly, this is not a 16-arm randomized control trial:** in factorial designs, subjects are “recycled,” allowing for the N per level (e.g. subjects randomized to loss-framing) to be the relevant value rather than the n per experimental condition.(Collins 2018) Effect coding will be used to represent each factor level (e.g. -1 for loss-framed and +1 for gain-framed).(Collins, Dziak et al. 2014) Effect coding allows effect estimates to be uncorrelated when the factorial study is balanced, which allows hypothesis tests to be independent.(Collins 2018) With effect coding, beta coefficient standard errors are equal, so in a balanced design, the power to detect each coefficient is the same.

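### The HbA1c category row names Fisher's exact test without stating the comparison; between factor levels that test is valid, but it leaves category order and Visit 1 category unused (minor)

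*Combined protocol and SAP*

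**What the plan says.** Table 1 (Analysis plan), placed under section 6.5.3, has two rows for HbA1c. One treats it as continuous together with the other laboratory measures ("Hemoglobin A1c, insulin, glucose, triglycerides, LDL, HDL, AST, ALT") and assigns ANOVA/ANCOVA. The other cuts it into three categories and reads "<5.7\%$ , $5.7\text{-}6.4\%$ , $\geq 6.5\%$ , Fisher's exact test". The category row names no visit, factor or contrast.

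Other sections bear on how to read it:

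- Section 2.2 frames the secondary objectives as "Determine the main and interactive effects of the four intervention components on" a list that includes HbA1c. Section 6.2 defines the endpoint for the laboratory measures as "change from visit 1 to visit 5 in" each of them.
- The Abstract says that "laboratory assessments will be assessed at two in-person study visits", so every completer has an HbA1c category at both visits.
- Section 3.5.1 admits participants with "Diagnosis with a condition associated with insulin resistance, including prediabetes or type 2 diabetes".
- Section 6.4 says multivariable models adjust for disease type and baseline laboratory values.
- In the same Table 1, the delay-discounting row specifies a "paired t-test or Wilcoxon signed rank test to assess whether baseline and follow-up measures differ".
- Section 6.5.1 sets the error rate: "The significance level for two-sided hypothesis testing will be set at 0.05".
- Section 6.6 claims at least 80% power for secondary outcomes including labs at a standardized coefficient of 0.36, with 64 evaluable participants. It makes no power claim for the category row.

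**The concern.** The row leaves the comparison open, and the choice of test depends on it. Three readings are possible: factor levels compared on Visit 5 category, factor levels compared on a change category (improved, same, worsened), or Visit 1 compared with Visit 5 over all participants.

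On the first reading, Fisher's test treats three ordered categories as unordered and has no place for where the participant started. The cut-points of 5.7% and 6.5% broadly separate the diagnostic groups that the trial enrols, so much of a participant's Visit 5 category is likely to be settled at Visit 1. Section 8.1.1 describes blocked randomization and states no stratification by diagnosis, so the mix will differ by chance between levels. On the third reading, the test would ignore that the same people are measured twice.

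Movement out of the diabetes or prediabetes range is an easily communicated glycaemic result. At stake is a real shift reported as non-significant for want of information already collected, and two analysts running different tests from the same line.

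**Working it through.** **1. The plan's own figure.** With -1/+1 effect coding, a coefficient of 0.36 is a difference between levels of 2 × 0.36 = 0.72 SD. With 64/2 = 32 per level, the noncentrality is 0.72 × √(32 × 32/64) = 0.72 × 4 = 2.88. The two-sided 0.05 t-test then has power 0.806 to 0.809 for 48 to 62 residual df, which reproduces the 0.80 in section 6.6. Because the endpoint is change, the SD in question is taken as that of the change.

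**2. Factor levels at Visit 5.** Assumptions, since the documents give none of these: a latent normal HbA1c with SD 1 at each visit, correlation ρ between visits, and cut-points at -0.6 and 0.4 (27%, 38% and 34% in the three categories at Visit 1). The SD of change is √(2(1-ρ)), so an effect of 0.72 change-SD on the Visit 5 scale is:

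- ρ = 0.5: 0.72 × 1.000 = 0.72
- ρ = 0.7: 0.72 × 0.775 = 0.56
- ρ = 0.9: 0.72 × 0.447 = 0.32

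The comparator is the Cochran-Mantel-Haenszel row-mean-score test. With scores 0, 1, 2 and strata h given by Visit 1 category, T_h is the score total in one level minus its expectation, V_h = (n1_h × n2_h/n_h) × s²_h, and Q = (ΣT_h)²/ΣV_h is referred to χ² on 1 df.

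| ρ | Fisher, Visit 5 | Ordered, stratified by Visit 1 | Gain |
|---|---|---|---|
| 0.5 | 0.60 | 0.78 | 0.18 |
| 0.7 | 0.40 | 0.68 | 0.28 |
| 0.9 | 0.16 | 0.43 | 0.27 |

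Null rejection was about 0.05 for both tests. At ρ = 0.5 ordering alone gives about 0.71, so 0.11 of the 0.18 comes from ordering and 0.07 from the Visit 1 category. With 2,000 replicates the simulation standard error is about √(0.6 × 0.4/2000) = 0.011; repeat runs differed by up to 0.02.

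**3. Does Fisher hold its error rate between levels?** Yes. Over single-population and mixture settings with ρ from 0.5 to 0.9, its type I error was 0.037 to 0.059.

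**4. A mixture closer to this trial.** Assumed: half prediabetes (mean 5.9, SD 0.3) and half type 2 diabetes (mean 7.5, SD 1.2), with a shift of 0.5 of each group's SD. Power for Fisher, ordered unstratified and ordered stratified was 0.19, 0.23 and 0.34 at ρ = 0.5, and 0.20, 0.22 and 0.39 at ρ = 0.7. Here most of the gain comes from the Visit 1 category.

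**5. Chance imbalance.** If 30% to 70% of participants have type 2 diabetes (assumed), the between-level difference in that share has SD √(2p(1-p)/32), which is 0.115 at p = 0.3 or 0.7 and 0.125 at p = 0.5. This is noise in the Visit 5 percentages, not bias.

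**6. Change category by level.** Fisher then uses both visits. At a 0.5 SD shift its power is 0.22 to 0.26 at ρ = 0.5, against 0.31 to 0.32 for Fisher on Visit 5 category in the single-population settings. At ρ = 0.9 it is 0.57 to 0.62, against 0.28 to 0.32.

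**7. Visit 1 versus Visit 5.** An unpaired Fisher test would count 64 pairs as 128 independent results. Its type I error was 0.000 to 0.019. At a 0.5 SD shift its power was 0.59 to 0.62 against 0.80 to 1.00 for Stuart-Maxwell in the single-population settings, and 0.25 to 0.26 against 0.64 to 0.79 in the mixture.

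**The case against.** The strongest reply is that nothing here is an error. Sections 2.2 and 6.2 describe effects of the components, so the natural comparison is between randomized levels. Those are independent participants, and Fisher's test is exact for them. Where the authors want a visit-to-visit test, the delay-discounting row names a paired one. Baseline is dealt with in the main HbA1c analysis through ANCOVA and section 6.4, and the category row is supplementary. All of this stands, and it limits the point to efficiency and clarity.

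Three stronger readings are tempting, and the documents do not support them:

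- A reader might infer that Fisher loses much of its power whichever comparison is meant. The change-category reading already uses both visits. For Visit 5 category, the part of the gain owed to the Visit 1 category is modest at a correlation of 0.5.
- A reader might infer that the plan applies an unpaired test to paired data. The row does not say so, and that reading is the least supported of the three.
- A reader might hold the effect at 0.72 of the Visit 5 SD for every correlation and find 0.59 against 0.97 at ρ = 0.9. That effect is 0.72/0.447 = 1.61 SD of the change, well above the 0.72 that section 6.6 implies. At the plan's effect the stratified test itself reaches only 0.43.

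The reply leaves two things unanswered. The row still does not say what it compares, and the Visit 1 category is collected but unused.

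**Conclusion.** The point holds as a minor one. For the comparison that the objectives imply, Fisher's test on Visit 5 category is valid but gives up about 18 points of power at an assumed visit correlation of 0.5, 28 at 0.7 and 27 at 0.9. This is for 32 per level and an effect of 0.72 SD of the change. At 0.5 more of the loss comes from ignoring order than from ignoring Visit 1; in the prediabetes/diabetes mixture the balance reverses. The sizes rest on assumed correlations, cut-points and mixture, none of which the documents supply. The direction was the same in every setting examined with a true effect.

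Only if Visit 1 versus Visit 5 were intended would the named test be wrong, and it would then be strongly conservative. Continuous HbA1c has its own ANOVA/ANCOVA row, so no main conclusion of the trial depends on this line.

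**What to change.** Replace the test in the HbA1c category row of Table 1 with wording such as: Visit 5 category (ordered: below 5.7%, 5.7 to 6.4%, 6.5% or above) compared between the two levels of each factor by a Cochran-Mantel-Haenszel row-mean-score test stratified by Visit 1 category, or by proportional-odds regression with Visit 1 HbA1c as covariate; any overall Visit 1 versus Visit 5 comparison by a paired test (exact sign test on category shift, or Stuart-Maxwell); the Visit 1 by Visit 5 shift table reported. Choose one of the two between-level methods in advance. The regression form also has room for the interactions named in section 2.2.

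The cost is one line of text and a few lines of Stata or R, with no new data or participants. The small downside is that sparse Visit 1 strata may need an exact or permutation version, which should be named at the same time.

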##### 3.1.3 Run-In

To determine baseline physical activity (MVPA), participants will be asked to wear the provided Fitbit for 14 consecutive days during waking hours and to sync the Fitbit daily with the app on their smartphone. They will also receive reminder text messages twice daily. Participants with mean daily MVPA >30 minutes or with < 4 days of Fitbit wear during the second week of run-in will be withdrawn from the study and will not continue on with the intervention. All participants will be called by phone (Visit 2) to review whether they will proceed to the intervention or not. Withdrawn participants will be asked to return the Fitbit using a prepaid envelop.

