### **3.1.5 Follow Up Study Visit (Visit 5)**

Within 2 weeks of completing the 12-week intervention, participants will be requested to return to PCTRCC for Visit 5 to obtain follow-up physical and biochemical data, as well as exit interview. Participants will be asked to fast for a minimum of 12 hours before the visit, and will be asked to return the Fitbit at study visit 5.

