## 4.3 Run-In and Randomization

### 4.3.1 2-Week Run-In

- Participant wears Fitbit daily during waking hours and syncs daily with smartphone
- Daily text message reminder sent to participant
- On day 15, study team will evaluate MVPA during days 8-14
  - Exclude from intervention if mean > 30 minutes/day or if < 4 days with evaluable Fitbit data
- Calculate mean daily step count during days 8-14, to provide to participant for reference

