## APPENDIX

### PACE+ Adolescent Physical Activity Measure

**Physical activity** is any activity that increases your heart rate and makes you get out of breath some of the time.

**Physical activity** can be done in sports, playing with friends, or walking to school.

Some examples of **physical activity** are running, brisk walking, rollerblading, biking, dancing, skateboarding, swimming, soccer, basketball, football, and surfing.

Add up all the time you spend in physical activity each day (don't include your physical education or gym class).

**P1** Over the past 7 d, on how many days were you physically active for a total of at least 60 min per day?

							
0 days	1	2	3	4	5	6	7 days

**P2** Over a typical or usual week, on how many days are you physically active for a total of at least 60 min per day?

							
0 days	1	2	3	4	5	6	7 days

Scoring:  $(P1 + P2)/2 < 5$  indicates not meeting physical activity guidelines.

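### At baseline, the PACE+ past-7-day item and the Fitbit count cover different weeks, and among randomised participants the Fitbit count cannot exceed 3 days, so a low baseline correlation is very likely whatever the true agreement

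*Combined protocol and SAP*

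**What the plan says.** The analysis-plan table in Section 6.5.3 lists the outcome as "PACE+: number of days with at least 60 minutes of activity per day in (a) past 7 days and (b) typical week". The planned analysis is a "Pearson/Spearman correlation with demographic variables and with number of days with MVPA" of at least 60 minutes, at baseline and at week 12.

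The Appendix gives the two items. The first asks "Over the past 7 d, on how many days were you physically active for a total of at least 60 min per day"; the second asks "Over a typical or usual week, on how many days are you physically active for a total of at least 60 min per day". Each is answered from 0 to 7 days. Respondents are told not to "include your physical education or gym class". Section 5.2 defines Fitbit MVPA by step rate alone, with no such exclusion.

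On timing, Section 4.2 puts the baseline questionnaires at Visit 1, and Sections 3.1.2 and 4.2 have the Fitbit handed out at that same visit. The Fitbit baseline comes later. Section 4.3.1 says "On day 15, study team will evaluate MVPA during days 8-14", and Section 3.1.3 says "Participants with mean daily MVPA >30 minutes or with < 4 days of Fitbit wear during the second week of run-in will be withdrawn". For follow-up, Section 3.1.5 says "Within 2 weeks of completing the 12-week intervention, participants will be requested to return", and Section 3.4.1 allows that window to be adjusted. The schedule of procedures marks surveys at follow-up, but the Visit 5 list in Section 4.5.1 names only the exit interview.

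The plan does not state which participants enter the baseline PACE+ correlation. It does not mention the difference in weeks, the gym-class difference or the restricted range.

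**The concern.** A correlation between a questionnaire and a device is read as a statement about agreement. That reading needs both to describe the same period and the sample to have enough spread for agreement to show. At baseline, the past-7-day item fails the first condition for everyone. If the analysis set is the randomised participants, the device count largely fails the second, because eligibility was decided on the same Fitbit week that supplies it. A low coefficient could then be taken as evidence that PACE+ performs poorly in this population, when timing and selection would be enough to produce it.

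What is at stake is small: one descriptive entry in the analysis table. No objective, endpoint or sample-size argument depends on it.

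**Working it through.** The documents give no figure for this correlation, so there is none to reproduce.

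**Step 1: overlap of windows for the past-7-day item.**
- Baseline: the recall covers the 7 days before Visit 1. The Fitbit is issued at Visit 1 and its baseline is run-in days 8-14. Overlap is 0 of 7 days, with at least run-in days 1-7 in between. Activity-planning coaching also takes place at Visit 1, between the two windows.
- Week 12: if PACE+ is repeated at Visit 5, which may fall 0-14 days after the intervention ends, the recall shares between 7 and 0 days with week 12, depending on the visit date.
- The typical-week item is tied to no calendar week, so no overlap can be computed for it.

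**Step 2: cap on the baseline Fitbit count.** Inputs are the 30 min/day limit and the minimum of 4 evaluable days (Section 4.3.1). If the mean over d evaluable days is at most 30, total minutes are at most 30 x d, and the number of days reaching 60 minutes is at most floor(30 x d / 60).

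| Evaluable days | Maximum total minutes | Maximum days of at least 60 min |
|---|---|---|
| 4 | 120 | 2 |
| 5 | 150 | 2 |
| 6 | 180 | 3 |
| 7 | 210 | 3 |

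The cap holds for observed days of participants who pass the run-in. It does not bind imputed days, participants excluded at run-in, or week 12.

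**Step 3: illustrative size.** 400,000 people were simulated. Person means were lognormal at 15, 25 or 35 min/day, within the 8-35 min/day that Section 1.3 reports for youth with type 2 diabetes. The between-person SD was 20 minutes, borrowed from Section 6.6. Daily minutes were gamma, with 7 evaluable days per week. Three inputs are assumptions with no source in the documents: a day-to-day coefficient of variation of 0.6 or 1.0, a reporting error of log-SD 0 or 0.5, and a week-12 shift of 0 or +15 minutes. Gym class was not modelled. Ranges run over all scenarios unless marked.

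| Comparison (Pearson r, days of at least 60 min) | Run-in mean of at most 30 only | No selection |
|---|---|---|
| Baseline, different week | 0.08-0.28 | 0.40-0.83 |
| Baseline, same week, with reporting error | 0.16-0.40 | 0.64-0.78 |
| Baseline, same week, no reporting error | 1.00 | 1.00 |
| Week 12, recall covers week 12, with reporting error | 0.38-0.61 | not run |
| Week 12, recall covers another week | 0.15-0.45 | not run |

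Among those retained, 73-99% have no baseline day of at least 60 minutes. At week 12 the largest simulated counts are 5-7 days.

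**Step 4: what the sample could detect.** With n = 64, two-sided alpha 0.05 and 80% power, the Fisher z approximation gives r = tanh((1.960 + 0.842)/sqrt(64 - 3)) = tanh(0.359) = 0.34. The whole 0.08-0.28 range lies below this.

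**The case against.** The strongest reply is that this is a minor descriptive entry and that much of the planned analysis escapes the criticism. Five parts of that reply deserve an answer.

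- **Scope of the cap.** A reader might infer that the run-in rule caps the Fitbit count throughout and makes the whole planned correlation weak by construction. The documents do not support that. The rule bears only on the run-in week of those who go on to be randomised. At week 12 the count can run from 0 to 7. Nor does the cap alone force a low value: in the simulation, the same week with no reporting error gives r = 1.00 despite the cap. This stands, and it limits the point to baseline.
- **The typical-week item.** It is half of the planned analysis and is tied to no calendar week. The window argument does not reach it; only the restricted range does.
- **Week 12.** A prompt Visit 5 would match week 12 well. Whether PACE+ is repeated there is itself unclear, since the schedule and the Visit 5 list differ. The mismatch is a possibility, not a certainty.
- **Analysis set.** The plan does not confine the baseline correlation to randomised participants, so the truncation is conditional. True, but the plan should then say who is included, because the answer largely determines the result.
- **Harm.** PACE+ is cited as already validated, and the only device-agreement objective in Section 2.2 is Fitbit against smartphone. This stands, and it is why the severity is low.

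What the reply does not remove is the certain non-overlap at baseline for the past-7-day item.

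**Conclusion.** The point holds at baseline, as a low-severity improvement. Two parts follow from the documents by arithmetic: the past-7-day item and the Fitbit baseline share 0 of 7 days, and randomised participants can have at most 3 observed days of at least 60 minutes, or 2 with 4-5 evaluable days.

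That the baseline correlation will be low is very likely but not proved. The 0.08-0.28 range rests on the assumed day-to-day variation and reporting error and on an analysis set of randomised participants only. At week 12 the value is open: it depends on the date of Visit 5 and need not be weak. The primary analysis, the secondary endpoints and the sample size are untouched.

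**What to change.** 1. Ask the PACE+ past-7-day item on the Visit 2 call, naming the calendar dates of run-in days 8-14. Dates are needed because Visit 2 may fall up to a week after run-in. Section 3.1.3 already has every participant called, including those being withdrawn.
2. Send the same item by REDCap link at the end of week 12, so that the recall covers week 12 whatever the date of Visit 5.
3. Correlate the item with mean daily MVPA minutes over the same 7 days, which avoids a mostly zero variable. Keep the count of days of at least 60 minutes as a secondary comparison, since it is in PACE+'s own unit. The simulation did not test the version using minutes.
4. Run the baseline correlation in all run-in completers with at least 4 evaluable days, including those excluded for MVPA above 30 min/day, and state that analysis set. In the simulation this matters more than aligning the week: with reporting error, aligning the week alone gives 0.16-0.40, whereas removing the selection alone gives 0.40-0.67.
5. State two limitations. PACE+ leaves out gym class, which the Fitbit counts, and no step above changes that. Recall after two weeks of wearing the device may also be informed by it, which could inflate agreement.

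The cost is one question on an existing call, one link and a few lines in Section 6.5.3, with about a minute of participant time on each of two occasions. The main downside is the possible device-informed recall. If no new data collection is wanted, the minimum is to state the analysis set and the recall window in Section 6.5.3 and to report the baseline coefficient with these limits.
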